4.2 Risk / Benefit analysis

While mechanical thrombectomy may speed time to reperfusion, like all therapies it carries risks. Through the EmboTrap device risk assessment process, a multi-functional team identified risks associated with the design, processing and use of the device, and identified the characteristics related to its safety.

All clinical risks were considered, including those identified through the Risk Management Report, and through the clinical literature search process. The risks listed below represent those identified as most clinically relevant through the literature review process.

- Abrupt vessel closure.
- Access complications.
- Access site pain, hematoma or hemorrhage.
- Allergic reaction to anticoagulants or antiplatelet therapy, contrast medium, or device material.
- Aneurysm or pseudo aneurysm.

- Arrhythmias, including VF and VT.
- Clot fragmentation during retrieval.
- Death.
- Delayed Recanalization.
- Device detachment.
- Emboli, distal (air, tissue or thrombotic emboli).
- Embolization of a previously unaffected vessel.
- Hemorrhagic Transformation.
- Hypotension/hypertension.
- Infection, local and/or systemic.
- Peripheral ischemia/peripheral nerve injury.
- Pulmonary edema.
- Renal failure.
- Respiratory failure.
- SAH - Subarachnoid Hemorrhage.
- Sedation complications.
- Shock.
- New Stroke/cerebrovascular accident/transient ischemic attack (TIA).
- Thrombus formation in the vessel (proximal, at the site of and distal).
- Total occlusion of cerebral vessel.
- Vasospasm.
- Vessel trauma, dissection, perforation, rupture or injury.

All efforts will be made to minimize the risks in this study by selecting investigators experienced and skilled in this interventional procedure and who have been trained in the ARISE II Study investigational protocol.

5 Subject selections

5.1 Enrolment

All consecutive patients who meet the inclusion and exclusion criteria will be enrolled.

5.2 Informed consent

Prior to admission to the study, a patient informed consent document will be given to each prospective subject or their Legally Authorized Representative (as defined by the local IRB or ethics committee), including an explanation of the study, duration, explanation of medical record access and patient anonymity, and how their coded data may be transferred, used for publications or in submissions for reimbursement support. The informed consent form will contain language that is non-technical and understandable to the patient or his/her legal representative.

The treatment occurs in an acute emergency situation, so locally required informed consent procedures may apply and will be complied with.

Each potential subject will be provided with written and verbal information regarding the nature of the study in an understandable manner. Adequate time will be allowed for the subject to consider participation in the clinical trial. Signed, written consent will be obtained from each subject prior to data collection and entry into the study. Any coercion or undue influence of potential subjects to participate must be avoided, and the subject's legal rights should not be waived. The investigator or an appropriately designated member of the study staff shall co-sign the consent form, indicating they believe the subject has understood the nature and risks of the study and, in their estimation, the subject clearly understands the scope of the consent. The investigator must inform subjects that they are in a controlled clinical trial, apprise them of their rights as set forth in the informed consent document, and make written documentation that such a discussion took place.

If the subject is not able to sign the informed consent, but has given his/her oral consent to participate, a third party can sign the informed consent for the subject. The procedure will be documented in the medical record. If the subject is not able to give his/her informed consent to participate in the study, a legally authorized relative or independent physician can sign the informed consent for the subject if this is approved by the local Institutional Review Board (IRB) or Ethics Committee (EC).

Short form informed consent may be utilized if approved by the IRB/EC. Each institution must follow their institutional IRB/EC policy for obtaining informed consent. If the short form informed consent is used, the summary must include all the basic elements of informed consent (21 CFR 50.25; ICH E64.8.10).

The procedure around how the informed consent is collected will be recorded in each subjects' medical record. The signed consent forms will be retained by the investigator and made available (for review only) to the study monitor and auditor on request.

Each site will maintain a log of all screened patients detailing the reasons for any subsequent patient exclusions or non-participation in the study. This could occur if angiographic inclusion and exclusion criteria are not met or if informed consent was withdrawn.

5.3 Subject withdrawals

Participation in this investigation is voluntary, and the subject may withdraw at any time. All enrolled subjects will be included in data analysis, unless they withdraw permission for their data to be used. The Sponsor will retain and continue to use any data collected prior to the withdrawal of consent, unless specified by the Subject or their Legally Authorized Representative.

In the event the subject chooses to withdraw, he/she will be instructed to contact the Investigator immediately. Withdrawal from the investigation will not affect the subject's follow-up care. The subject will be informed of any significant information regarding new findings that may develop

during the course of the research study that may relate to his or her willingness to continue participation as a study subject.

Subjects will participate in their routine follow-up and allow this data to be gathered or their participation in the study will be prematurely terminated. If their participation is terminated, any of their data which has been already gathered will continue to be included. The completion of a subject's participation in the study or early departure from the study must be fully documented in the subject's study progress notes.

Subjects will be considered discontinued from the study if any of the following occur:

- Death or intercurrent illness: If, during the conduct of the study, a subject dies or experiences an intercurrent illness, all available information should be obtained and an appointed Neuravi representative/ study monitor should be notified no more than 24 hours from study staff becoming aware of the event.
- If a subject's death occurs while in the hospital, submit a copy of the physician's death summary report. If an autopsy is performed, submit a copy of the autopsy report, as well. If a subject's death occurs outside of the study site, obtain all information related to the death and submit the investigator's summary of the events associated with the death.
- Subject voluntarily withdraws from the study: A subject may withdraw consent from study participation at any time.
- Subject withdrawn from the study by the investigator: An investigator may withdraw an enrolled subject from the study for the following reason:

Protocol violation: Should a subject be enrolled but later determined ineligible based on previously unavailable source documentation or due to a violation in following the protocol at the study site, this subject will be considered a protocol violation. This subject's data will not be pooled for statistical analysis with those subjects confirmed to be eligible by the investigator and the appointed study monitor for Neuravi. All protocol violations should be documented by the study monitor appointed by Neuravi.

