8.3.2 Intention to Treat

All subjects confirmed to meet the inclusion and exclusion criteria via angiography in the ARISE II Study will be included in the ITT analysis of safety and effectiveness, as data allows.

8.3.2.1 *Modified Intention To Treat*

In order to analyze a comparable population to that used in the predicate studies, SWIFT and TREVO II, the primary hypothesis will also be tested on a “Modified Intention to Treat” (mITT) subgroup. The mITT subgroup will reflect the lytic regime used in the TREVO II and SWIFT studies.

- This subgroup will exclude screen failures for inclusion criterion 11.
- This subgroup will have been treated in compliance with the protocol and will meet the lytic regime requirements set out in inclusion criteria 7 and 8.
- And only patients who are contra-indicated for IV-tPA or in whom IV-tPA has failed will be included in the mITT analysis. Failure of IV-tPA is defined as angiographic evidence of persistent target vessel occlusion, one hour or more after the initiation of IV-tPA therapy.

The cut off time point for initiation of lytic therapy will be in line with the FDA approved time indicated which is within 3 hours of stroke onset. All patients who meet the study entry criteria, are enrolled in the trial and were treated per the protocol (introduction of rescue therapy prior to three retrieval attempts with EmboTrap is a protocol violation) will be included in the mITT analysis sample. It is expected this will include most of the ARISE II population and the facility to enroll up to 228 should ensure that an evaluable sample of 176 are available for the mITT analysis.

8.3.3 *Analysis of the Secondary endpoints*

All other binary endpoints will be treated using the Wilson exact Binomial Proportion test to allow a statement on the corresponding population proportion be made.

Descriptive statistics will be used to summarize the clinical outcome variables collected on all vessels treated in this investigation overall and for each center.

The typical value for each continuous response variables will be estimated using the mean and median while the variability will be estimated using the range, interquartile range and standard deviation. All categorical variables will be reported as counts and percentages.

Box and bean plots will be generated for each continuous response variables while bar charts will be generated for each categorical variable.

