8.3.5 Deviations from the statistical plan

Any departure or deviation from these planned statistical methodologies will be documented and discussed in the Statistical Analysis Plan that will include the statistical rationale for change.

9 Amendment to the CIP

Only Neuravi is allowed to modify this protocol. The change will be in the form of a protocol amendment. Any modification that potentially affects subjects' rights or safety must also be approved by the EC or IRB and other regulatory agencies. In an emergency situation, where action is necessary to protect the life or physical wellbeing of the subject, a departure from the protocol for an individual subject may be allowed, and that departure will be for that subject only. In such circumstances, the investigator must notify the EC or IRB and Neuravi and must describe the conditions necessitating the departure from the protocol and the outcome of the emergency intervention in a written report. Neuravi will determine whether the subject is to continue in the study or be considered a protocol violation.

10 Deviations from the CIP

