5.1 Study objectives

The study objective is to examine the recanalization efficacy of the EmboTrap device and its associated performance characteristics and to record associated clinical outcomes in a

manner that facilitates relevant comparison of outputs with that of devices approved in the U.S. for clearing Large Vessel Occlusions.

5.2 **Study endpoints**

5.2.1 **Primary Efficacy endpoint**

The primary efficacy endpoint of the study is revascularization measured using modified Thrombolysis in Cerebrovascular Infarction (mTICI inclusive of the 2c rating). Successful achievement of the endpoint is defined as achieving an mTICI score of 2b or greater in the target vessel, following 3 or less passes of the EmboTrap device. The mTICI result will be based on the final angiogram after the total number of EmboTrap passes performed up to the maximum 3 passes allowed as adjudicated by the Core Lab or the final angiogram after attempted recanalization with the EmboTrap Revascularization Device if rescue devices were used.

Use of rescue therapy, prior to taking the primary endpoint angiogram, is a protocol violation and the resultant angiogram outcomes will be considered failures to achieve the primary endpoint irrespective of mTICI score.

In this single arm study physicians were not precluded from using rescue therapy in the patient post completion of the Primary Efficacy imaging angiogram, this is because more than one vessel, or a previously not visible distal occlusion, may require treatment to achieve a patient optimum outcome. If the physician had a preference for using a smaller device to treat the patient in a distal location or in another vessel this was not precluded.

In a randomised study where both devices would be similarly treated in terms of the use of rescue therapy, and the options for rescue therapy are more limited, a different approach may have been appropriate. As ARISE II was conducted over two continents there were a wide range of device options available to European interventionalists. It would not be appropriate to diminish the efficacy rate reported for EmboTrap by moving all scores of 2b achieved within 3 passes to consider them fails if the interventionalist chose to continue to treat the patient with an alternative device in line with the guidance in the study protocol.

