7.1 Missing and Censored Data

An extra 30% to the required evaluable patient cohort number is included to bring the total cohort to 228. Missing data will be examined, and the reasons will be investigated and reported.

Missing data for the primary endpoint might be expected in the case of patients eligible for treatment (ITT) but receiving no treatment and thus would have no angiography during procedure from which to make a determination of mTICI. For the primary efficacy outcome, a simple sensitivity analysis of the ITT population will be carried out to assess the robustness

of the conclusions on this endpoint to missing data (see Section 10.3). No missing data is expected for the primary safety outcome and no imputation will be performed for missing data on secondary outcomes. Results measured outside the protocol prescribed time windows, will be treated as missing data.

8 *Timing of analyses*

8.1 *Interim analyses*

There are no planned interim analyses for this study.

8.2 *Final analyses*

All final analyses identified in this SAP will be performed after the last patient has completed the study. Before carrying out the analyses, the data management team is responsible for the database cleaning process to ensure the integrity of the analyses. No database may be locked or analyses completed until the SAP has been approved and the database will be locked prior to the initiation of the analysis. Key statistics and study results will be made available following database lock and prior to completion of the final Clinical Study Report (CSR).

Any post-hoc exploratory analyses completed to support planned study analyses, which were not identified in this SAP, will be documented and reported in appendices to the CSR.

9 *Analysis populations*

The primary efficacy endpoint will be examined for the following cohorts, An Intention to Treat cohort, a modified Intention To Treat cohort created to select a data set relevant to FDA lytic labelling constraints relevant at the time of study execution, a Per Protocol cohort, and a Treated Set cohort, which mirrors the protocol, and excludes any violations. The primary population for test will be the ITT.

9.1 *Intention to Treat*

Intention to Treat (ITT): Will include all patients who meet all angiographic eligibility criteria.

- The primary analysis for the primary efficacy endpoint will be performed on subjects in the ITT cohort with non-missing mTICI assessments.

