Per Protocol (PP): Defines a cohort of subjects who meet all eligibility criteria and are treated with the Embotrap device. Patients with protocol violations will be excluded from analysis.

In order to provide additional context to the results observed in the ITT cohort,

- The analysis of the primary efficacy endpoint will be repeated on patients in the PP cohort with non-missing mTICI assessments.
- The analysis of the primary safety endpoint will be repeated on patients in the PP cohort.

9.4 *Treated Set*

Treated Set (TS): Defines a cohort of subjects who are treated with the EmboTrap device regardless of study eligibility. In order to provide additional context to the results observed in the ITT cohort,

- The analysis of the primary efficacy endpoint will be repeated on patients in the TS set with non-missing mTICI assessments.
- The analysis of the primary safety endpoint will be repeated on patients in the TS set.

10 General issues for Statistical Analysis

10.1 *Software used for the analysis*

All Primary and secondary statistical analyses will be validated by an independent statistician, or using independent software (R, SAS, SPSS, Minitab or Stata). All of the code generated will be kept by both the study statistician and the independent statistician.

10.2 *Confidence intervals*

All confidence intervals reported for binary variables will be Wilson exact binomial confidence intervals and for continuous variables will be based on a normal distribution assumption for the parameter of interest.

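### Protocol 5.3 keeps protocol violators out of the pooled analysis without naming an analysis set, which conflicts with the SAP's ITT and Treated Set and could bias the primary test if applied to ITT

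*Protocol*

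**What the plan says.** **Protocol 5.3** begins: "All enrolled subjects will be included in data analysis, unless they withdraw permission for their data to be used". It adds that data already gathered stay in if participation is terminated. It then lists protocol violation as a ground on which the investigator may withdraw an enrolled subject: "Should a subject be enrolled but later determined ineligible based on previously unavailable source documentation or due to a violation in following the protocol". Such a subject's "data will not be pooled for statistical analysis with those subjects confirmed to be eligible by the investigator and the appointed study monitor".

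**Protocol 9** deals with emergency departures from the protocol and gives the sponsor a further decision: "Neuravi will determine whether the subject is to continue in the study or be considered a protocol violation".

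**Protocol 8.3.2** defines ITT through eligibility: "All subjects confirmed to meet the inclusion and exclusion criteria via angiography in the ARISE II Study will be included in the ITT analysis".

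**SAP 9.1** defines ITT, the primary population, through the angiographic criteria alone: "Will include all patients who meet all angiographic eligibility criteria". The primary safety analysis uses the treated subjects in that set. **SAP 9.3** (Per Protocol) is the set that drops violators. **SAP 9.4** describes the Treated Set: "Defines a cohort of subjects who are treated with the EmboTrap device regardless of study eligibility". The lead-in to SAP section 9, however, describes the Treated Set as leaving violations out.

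**SAP 5.2.1**, like protocol 3.3, states: "Use of rescue therapy, prior to taking the primary endpoint angiogram, is a protocol violation and the resultant angiogram outcomes will be considered failures". Protocol 10.1 and SAP 11.2 both list early rescue as a violation.

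**The concern.** The exclusion in 5.3 is not tied to any analysis set, has no deadline, and need not be made without knowledge of the outcome. The trial is open label with a single arm. The endpoint angiogram is taken during the procedure, after at most three passes (protocol 6.5.1.1.5). Pooling depends on eligibility being confirmed by the investigator and the study monitor, and the monitoring visits in protocol 14 follow the first and fourth enrolments. A decision to exclude can therefore come after the operator has seen the result, even if core-laboratory adjudication is still pending.

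One kind of violator is a failure by definition: the patient given rescue before the endpoint angiogram. If that patient is not pooled, the failure is not counted, and the success rate tested against 0.56 rises. This is the trial's only hypothesis test. Because the safety denominator is the treated part of ITT, it would change too.

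**Working it through.** **1. Do the rules agree?**

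| Rule | Subject later found ineligible | Subject with a conduct violation |
|---|---|---|
| Protocol 5.3, opening | In | In |
| Protocol 5.3, violation paragraph | Not pooled | Not pooled (on one reading) |
| Protocol 8.3.2 ITT | Arguably out | Silent |
| SAP 9.1 ITT | In, if angiographic criteria met | In, if angiographic criteria met |
| SAP 9.3 Per Protocol | Out | Out |
| SAP 9.4 Treated Set | In, if treated | In, if treated |
| SAP 9 lead-in, Treated Set | Out | Out |
| SAP 5.2.1, early rescue | Not applicable | In, counted as failure |

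The violation paragraph of 5.3 cannot hold together with the opening of 5.3, SAP 9.1, SAP 9.4 or SAP 5.2.1. Protocol 8.3.2 (for ineligible subjects) and the SAP 9 lead-in lean towards it.

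**2. Reproduce the plan's figure.** Inputs from protocol 8.2 and SAP 7: n = 176, limit 0.56, assumed rate 0.68, one-sided exact binomial test at 0.025. The cut-off is the smallest r with P(X ≥ r | n, 0.56) ≤ 0.025.
- r = 112 (112/176 = 63.6%), with exact type I error 0.0240.
- Power at 0.68: P(X ≥ 112 | 176, 0.68) = 0.906, and 176 is the first n that reaches 90%. The plan's figure reproduces.
- Requiring the Wilson 95% lower bound to exceed 0.56 gives the same r = 112.

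**3. How few removals change the result?**
- 110/176 = 62.5% fails (p = 0.048). Remove 4 failures: 110/172, where the cut-off is 110, passes (p = 0.021).
- 108/176 = 61.4% fails (p = 0.087). Remove 7 failures: 108/169, where the cut-off is 108, passes (p = 0.022).

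Both examples require every removed patient to be a failure.

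**4. False-pass rate under assumed removal.** The documents give no number of violators and no success rate among them, so both are assumed. Let v be the fraction removed and s the success rate among those removed, with a true rate of 0.56 in all patients. The number removed is Binomial(176, v). The rate among those kept is (0.56 − v·s)/(1 − v), and each kept n is tested at its own exact cut-off.

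| v | s | Rate among kept | False-pass rate |
|---|---|---|---|
| 0 | – | 0.560 | 2.4% |
| 3% | 0.56 (unrelated to outcome) | 0.560 | 2.1% |
| 5% | 0.56 (unrelated to outcome) | 0.560 | 2.1% |
| 3% | 0.30 | 0.568 | 3.4% |
| 5% | 0.30 | 0.574 | 4.6% |
| 3% | 0 | 0.577 | 5.7% |
| 5% | 0 | 0.589 | 10.2% |

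For example, with v = 5% and s = 0: 0.56/0.95 = 0.589. Removal unrelated to outcome does not inflate the error. The harm comes only from selective removal.

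**5. Safety.** The effect depends on who is removed. With an assumed 12 events in 176 (6.8%), removing three patients with events gives 9/173 = 5.2%. Removing three without events gives 12/173 = 6.9%.

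**The case against.** **The SAP largely deals with this.** It was written against protocol revision 05 and does not carry 5.3 into ITT. It defines ITT by angiographic eligibility, drops violators only in Per Protocol, scores early rescue as failure and, in 9.4, reports all treated patients. This stands: the bias arises only if 5.3 is applied over the SAP, and no text says that it should be. But no text says that it should not be, and the SAP appends the protocol, so an analyst could follow either rule.

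**The wording of 5.3 can be read narrowly.** The violation clause may qualify only how a subject was found ineligible, data kept out of pooling need not be discarded, and data already gathered are to be retained. These readings are open. They reduce the reach of the rule but leave it ambiguous, and exclusion for ineligibility found after treatment remains.

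**Exclusion is not purely discretionary.** It rests on source documents and monitor confirmation, with full source verification (protocol 15.1), and protocol 9 concerns emergencies only. That limits abuse but does not make the decision blind to outcome.

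**A reader might infer more than the documents support.**
- *That 5.3 removes bleeds and so understates harm.* No passage links violators to haemorrhage, so the direction for safety is not established.
- *That exclusions will be made with knowledge of the outcome.* The text says that ineligibility is determined later; knowledge of the outcome is possible, not stated.
- *That follow-up stops.* Such a subject counts as discontinued, but the section does not say that visits end, and protocol 12.3.1 collects adverse events to day 90 for enrolled patients.

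**Conclusion.** The textual conflict is certain. The bias is conditional on 5.3 being applied to the ITT set. In that case overstated efficacy has a documentary basis, because early-rescue violators are failures by definition. For other violators the direction is not known.

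The range in step 4, from no inflation to about four times the planned error, rests on assumed removal of 3% to 5% and assumed success rates. It shows sensitivity and is not a forecast. The zero-success rows describe a group made up entirely of failures, such as early-rescue patients, whom the SAP as written keeps and counts.

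The documents do not support a claim that the plan as a whole removes failures and bleeds. The point is worth correcting because a handful of exclusions can decide the sole test and the correction needs only wording.

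**What to change.** - **Protocol 5.3:** state that exclusion for a protocol violation applies to the Per Protocol set only. Keep every angiographically eligible patient in ITT and every treated patient in the Treated Set, for efficacy and safety, with scheduled data collection to day 90. Make an exception where consent is absent or withdrawn, since failure to obtain consent is itself a listed violation.
- **Classification:** have all violations, including the sponsor's decisions under protocol 9, classified before database lock without sight of mTICI or clinical outcome.
- **Reconcile** the two statements in protocol 5.3, the ITT wording in protocol 8.3.2 and SAP 9.1, and the two descriptions of the Treated Set in the SAP 9 lead-in and SAP 9.4.

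Cost: protocol and SAP wording, with no extra patients or visits. The headline success rate may be slightly less favourable than if violators were left out.
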